10.2 Efficacy Analyses

Data collected at any point prior to the specified cutoff date during the study will be used in efficacy analyses, unless otherwise specified.

10.2.1 Primary Efficacy Analysis

The primary efficacy endpoint will be complete remission rate (CR + CRi) of the subjects in ITT-BN population defined in Section 5.1.1.

In addition, the ninety-five percent (95%) confidence interval based on the Clopper-Pearson exact method for binomial distribution will be constructed for the calculated CR rate.

10.2.2 Secondary Efficacy Analyses

ORR will be assessed as the proportion of subjects with an overall response (CR + CRi + nPR + PR) based on the IWCLL NCI-WG criteria. The ninety-five percent (95%) confidence interval based on the Clopper-Pearson exact method for binomial distribution will be constructed for the calculated ORR rate.

DOR, TTP, PFS, and OS will be analyzed by Kaplan-Meier methodology using data for all subjects defined in Section 5.1.1. Median time of each endpoint will be calculated and 95% confidence interval for median time of each endpoint will be presented.

The analyses of ORR, DOR, TTP, PFS, and OS will be performed on ITT, ITT-BN, and ITT-BE population.

The complete remission (CR + CRi) rate in will be assessed based on the 2008 Modified IWCLL NCI-WG criteria for ITT and ITT-BE population. The ninety-five percent (95%) confidence interval based on binomial distribution will be constructed for the calculated complete remission rate.

10.2.3 Exploratory Efficacy Analysis

The rate of MRD negativity in subjects will be summarized. This rate will be defined as the proportion of subjects who had MRD negativity status in peripheral blood. Ninety-five percent (95%) confidence intervals based on the Clopper-Pearson exact method for binomial distribution will be provided.

10.3 Additional Secondary Efficacy Analyses

Additional efficacy endpoints to be analyzed for the ITT, ITT-BN, and ITT-BE populations are Health Economic and Patient Reported Outcome measures, which include the FACT-Leu, FACIT-F, and the EQ-5D-5L (measure of general health status) and EQ-5D-VAS (Visual Analog Scale).

For the FACT-Leu, scores will be summarized descriptively at each assessment. The impact of treatment on quality of life over time will be assessed by calculating the change in scores from baseline at each assessment time point. Scores will be calculated according to the FACT-Leu scoring manual. The scores will also be summarized (mean, standard deviation, median) at each assessment. In addition mean change in scores (each assessment versus baseline) will be estimated. The 95% confidence interval of the mean change will be constructed based on (a) paired t-test and (b) with model assumption. A

linear mixed effect model will be used for the analysis of repeated measures where the covariance pattern will be assumed as compound symmetry (CS).

For the FACIT-F, scores will be summarized descriptively at each assessment. The impact of treatment on fatigue over time will be assessed by calculating the change in score from baseline at each assessment time point. Scores will be calculated according to the FACIT-F scoring manual. The scores will also be summarized (mean, standard deviation, median) at each assessment. In addition mean change in scores (each assessment versus baseline) will be estimated. The 95% confidence interval of the mean change will be constructed based on (a) paired t-test and (b) with model assumption. A linear mixed effect model will be used for the analysis of repeated measures where the covariance pattern will be assumed as compound symmetry (CS).

The EQ-5D-5L is a generic preference instrument that has been validated in numerous populations. The EQ-5D-5L has five dimensions: mobility, self care, usual activities, pain/discomfort and anxiety/depression. These dimensions are measured on a five level scale: no problems, slight problems, moderate problems, severe problems, and extreme problems. The EQ-5D-5L also contains a visual analog scale (VAS) to assess the subject's overall health.

For each of the five dimensions of the EQ-5D-5L, the number and percentage of subjects at each level will be summarized at each assessment. The VAS values and the score of the EQ-5D-5L will also be summarized (mean, standard deviation, median) at each assessment; in addition mean change in VAS values and the score of the EQ-5D-5L (each assessment versus baseline) will be estimated. The 95% confidence interval of the mean change will be constructed based on (a) paired t-test and (b) with model assumption. A linear mixed effect model will be used for the analysis of repeated measures where the covariance pattern will be assumed as compound symmetry (CS).

10.4 Subgroup Analyses of Efficacy and Quality of Life

To evaluate the impact of baseline conditions on efficacy, subgroup analyses will be performed for complete remission (CR + CRi) in the ITT, ITT-BN, and ITT-BE population.

The following subgroups below will be used for efficacy analyses:

- Sex (male, female)
- Race (White, Non-White)
- Age (< 65, ≥ 65; < 75, ≥ 75)
- ECOG status (0, 1, 2)
- 17p deletion status (deleted, not-deleted)
- TP53 mutation status (yes, no)
- Prior number of oncology therapies (1, 2, ≥ 3)
- Baseline ALC (< $25 \times 10^9/L$, ≥ $25 \times 10^9/L$; < $100 \times 10^9/L$, ≥ $100 \times 10^9/L$)
- Baseline node size (< 5 cm, 5 cm To 10 cm, ≥ 10 cm)

ORR and CR and their 95% CIs will be reported for each level of subgroups in a forest plot. KM plot for DOR, and PFS will be also be provided for 17p deleted versus non-17p del., TP53 mutation versus TP53 non-mutation, and prior BCRi treated versus prior BCRi naïve. MRD response rate will be additionally summarized by overall response category (CR/PR/non-responders) and the BCRi failure status (yes, no).

The following subgroups below will be used for quality of life analyses:

- 17p deletion status (deleted, not deleted)
- TP53 mutation (yes, no)
- Prior BCRi treated (yes, no)
- Prior number of oncology therapies (1, 2, ≥ 3)
- Baseline ALC (< $25 \times 10^9/L$, ≥ $25 \times 10^9/L$; < $100 \times 10^9/L$, ≥ $100 \times 10^9/L$)
- Baseline node size (< 5 cm, 5 cm to 10 cm, ≥ 10 cm)

- Hospitalized for TLS prophylaxis before venetoclax (yes, no)

10.5 Handling of Multiplicity

There will be no multiplicity adjustments performed.

11.0 Safety Analysis

11.1 General Considerations

Safety data will be summarized for the ITT population.

11.2 Analysis of Treatment-Emergent Adverse Events

All summaries/analyses involving AEs will include treatment-emergent adverse events (TEAE) only, unless otherwise specified. TEAE are defined as any event with onset after the first dose of venetoclax and no more than 30 days after the last dose of venetoclax. Events where the onset date is the same as the venetoclax start date are assumed to be treatment-emergent, unless the venetoclax start time and the AE start time are collected and the AE start time is prior to the venetoclax start time. If an incomplete onset date was collected for an AE, the AE will be assumed to be treatment-emergent unless there is evidence that confirms that the AE was not treatment-emergent (e.g., the AE end date was prior to the date of the first dose of venetoclax).

Treatment-emergent adverse events will be summarized by maximum severity grade level of each preferred term. Each adverse event will be assigned a grade level (grade 1, 2, 3, 4, or 5) by the investigator. If a subject has an AE with unknown severity, then the subject will be counted in the severity grade level category of "unknown," even if the subject has another occurrence of the same event with a severity present. The only exception is if the subject has another occurrence of the same AE with the highest grade level (grade 5). In this case, the subject will be counted under the "Grade 5" category.

Treatment-emergent adverse events will be summarized by relationship of each preferred term to venetoclax, as assessed by the investigator. If a subject has an adverse event with

unknown relationship, then the subject will be counted in the relationship category of "unknown," even if the subject has another occurrence of the same event with a relationship present. The only exception is if the subject has another occurrence of the same adverse event with a relationship assessment of "Reasonable Possibility." In this case, the subject will be counted under the "Reasonable Possibility" category.

Adverse events will be coded using the Medical Dictionary for Regulatory Activities (MedDRA). The actual version of the MedDRA coding dictionary will be noted in the clinical study report.

Adverse event data will be summarized and presented using primary MedDRA system organ classes (SOCs) and preferred terms (PTs) according to the MedDRA coding dictionary version 20.1 or higher.

Adverse Event

An overview of AEs will be presented consisting of the number and percentage of subjects experiencing at least one event for each of the following AE categories:

- Any treatment-emergent adverse event;
- Any treatment-emergent adverse event with reasonable possibility related to venetoclax by the investigator;
- Any treatment-emergent NCI toxicity (CTCAE V4.03) grade 3, 4, or 5 adverse events;
- Any treatment-emergent NCI toxicity (CTCAE V4.03) grade 3 or 4 adverse event;
- Adverse events broken down by NCI toxicity grade (Severity);
- Any treatment-emergent serious adverse event;
- Any treatment-emergent adverse event leading to discontinuation of venetoclax;
- Any treatment-emergent adverse event leading to venetoclax interruption
- Any treatment-emergent adverse event leading to venetoclax reduction

- Any treatment-emergent adverse event leading to death;

For summary tables of AE by PT, subjects reporting more than one AE for a given PT will be counted only once for that term (most severe/highest grade incident for the severity tables and most related incident for the relationship tables). Subjects reporting more than one AE within an SOC will be counted only once for that SOC. Subjects reporting more than one AE will be counted only once in the overall total.

Adverse Events of Special Interest

Adverse events of special interest will be summarized. The list of adverse events of special interest is shown in [Table 3](#).

For each of the adverse event of interest, the number and percentage of subjects experiencing at least one treatment-emergent adverse event will be presented overall and by SOC and PT. In addition, a listing of treatment-emergent adverse events for subjects meeting each of the search criteria will be provided.

Table 3. Adverse Events of Special Interest

Risk	Search Criteria
Tumor Lysis Syndrome (three searches)	
 1) SMQ – "Tumour lysis syndrome" (Narrow-scope) 2) SMQ – "Tumour lysis syndrome" (Narrow) plus PT terms of "Hyperkalaemia," "Hyperuricaemia," "Hyperphosphataemia," "Hypocalaemia," "Blood potassium increased," "Blood uric acid increased," "Blood phosphorus increased," "Blood calcium decreased" 3) SMQ – "Tumour lysis syndrome" (Narrow) plus broad-scope terms with algorithm applied (i.e., two events from category B and one event from category C required for a subject to be counted as having a TLS event)
Neutropenia	PT terms – "Neutropenia," "Neutrophil count decreased," "Febrile neutropenia," "Agranulocytosis," "Neutropenic infection," and "Neutropenic sepsis"
Serious Infection, Including Opportunistic Infections	SAEs in the SOC of "Infections and Infestations"
Second Primary Malignancy	SMQ – "Malignant tumours" (Narrow) and "Myelodysplastic syndromes" (Narrow)
Lymphopenia	PT terms – "Lymphopenia" and "Lymphocyte count decreased"
Anemia	PT terms – "Anaemia" and "Haemoglobin decreased"
Thrombocytopenia	PT terms – "Thrombocytopenia" and "Platelet count decreased"
Drug Induced Liver Injury (DILI)	SMQ – "Drug related hepatic disorders – comprehensive search"
Medication Error	SMQ – "Medication error" (broad)

SMQ = Standardised MedDRA Query

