Subjects may have 17p deletion and/or TP53 mutation as assessed by local laboratory (in bone marrow or peripheral blood) to be considered as having this deletion/mutation. However, the 17p deletion or TP53 mutation is not a protocol required test for subjects to be enrolled in this study. If a subject does have the 17p deletion or TP53 mutation, a recent test is desirable but any previous positive test is acceptable.

Medical and Oncology History

A complete medical history, including history of tobacco, nicotine-containing products and alcohol use, will be taken from each subject during the Screening visit, including:

- documentation of any clinically significant medical condition
- a detailed oncology history including:
 - histology
 - cytogenetics
 - date of CLL diagnosis
 - stage
 - any surgical procedures
 - treatments administered (including dates, type of modality, response to treatment and reason for treatment discontinuation)

On Week 1 Day 1, any additional medical history observed after signing of the informed consent but prior to initial venetoclax administration and not considered related to study-required procedures will be recorded in the subject's medical history.

Pregnancy Testing

- WOCF must have a negative serum pregnancy test result at Screening, and a negative urine pregnancy test at Study Day 1.
- Screening – quantitative beta-human chorionic gonadotropin (β -hCG) serum pregnancy test.
- Week 1 Day 1: Urine test, if it has been > 7 days since obtaining the Screening serum pregnancy test results.
- During the study a urine pregnancy test can be performed at the discretion of the investigator or per local guidelines.
- Females of non-childbearing potential (either postmenopausal or permanently surgically sterile as defined in Inclusion Criterion 9) at Screening do not require pregnancy testing.

Adverse Event and Concomitant Medication Assessment

On Week 1 Day 1, any protocol-related events observed from the time of signing of the informed consent but prior to initial venetoclax administration will be recorded as a serious or nonserious adverse event, if considered by the investigator to be causally related to the study-required procedures (See [Figure 3](#)).

At each visit, including the Final Visit and the Post-Treatment Follow-Up, the subject's medical history will be reviewed and any changes from baseline will be recorded on the adverse event eCRF.

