6.1.4 Adverse Event Collection Period

All adverse events reported from the time of venetoclax administration until 30 days, following discontinuation of venetoclax administration have elapsed will be collected, whether solicited or spontaneously reported by the subject. In addition, protocol related serious adverse events and nonserious adverse events will be collected from the time the subject signed the study-specific informed consent.

All AEs should be followed until resolution, return to baseline or determined to be stable per the investigator.

Adverse event information will be collected as shown in [Figure 3](#).

Figure 3. Adverse Event Collection

* Only if considered by the investigator to be causally related to study-required procedures.

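### The SAP names second primary malignancy as an event of special interest, but onsets more than 30 days after the last dose reach no adverse event summary or listing, and the protocol conflicts on whether sites record them

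*SAP*

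**What the plan says.** **Analysis.** SAP 11.2 sets the default: "All summaries/analyses involving AEs will include treatment-emergent adverse events (TEAE) only, unless otherwise specified". A treatment-emergent event is "any event with onset after the first dose of venetoclax and no more than 30 days after the last dose of venetoclax". Table 3 includes "Second Primary Malignancy" with its own search criteria. For every event in that table, "the number and percentage of subjects experiencing at least one treatment-emergent adverse event will be presented overall and by SOC and PT", and "a listing of treatment-emergent adverse events for subjects meeting each of the search criteria will be provided". No other window is given for malignancy. Protocol 8.1.5.1 applies the same 30-day cut.

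**Follow-up.** Protocol 5.3.1.1 and 5.4.1 provide calls every 6 months for 2 years after venetoclax stops.

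**Collection.** Protocol 6.1.4 reads: "All adverse events reported from the time of venetoclax administration until 30 days, following discontinuation of venetoclax administration have elapsed will be collected". Section 5.4.1 and the footnotes on post-treatment follow-up in Appendices D and E describe the calls as gathering survival information: date and cause of death, later cancer therapies and, in 5.4.1, progression. Section 5.3.1.1 says something wider: "At each visit, including the Final Visit and the Post-Treatment Follow-Up, the subject's medical history will be reviewed", with any change from baseline entered on the adverse event form. The Post-Treatment Follow-Up columns of Appendices D and E mark the adverse event assessment as due.

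**The concern.** Thirty days after the last dose is a normal default for adverse events in general. It suits a second cancer less well, because a cancer may be diagnosed months after a subject stops. The SAP singles this event out but gives it the general window, although later contacts are already scheduled.

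Two things are at stake. First, a later cancer is left out of the special-interest table and listing even when a site has entered it. Second, two sites can each follow a passage of the protocol and record different things after day 30, so a later attempt to widen the count may rest on uneven data. The protocol's own special-interest section (6.1.1.4) names tumor lysis syndrome, neutropenia and serious infection only, so it does not prompt sites to ask about new cancers.

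**Working it through.** The documents state no rate or count for second malignancies, so there is no figure to reproduce. The check is of windows and of text.

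**Inputs**
- Count window: days on drug + 30 (SAP 11.2).
- Off-drug follow-up: 2 years, taken as 730 days (protocol 5.3.1.1, 5.4.1).
- Main-phase treatment: up to 2 years, taken as 730 days (protocol synopsis).
- Last cutoff in SAP Table 1: 30 April 2018.
- Original protocol date: 24 February 2016 (protocol 1.1).

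**1. Full follow-up.** Uncounted days = 730 − 30 = 700, which is 700/730 = 95.9% of off-drug follow-up. Uncounted share of all observation = 700 / (days on drug + 730).

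**2. The last dated cutoff.** From 24 February 2016 to 30 April 2018 is 731 + 65 = 796 days. No subject can have been observed longer than that, so uncounted days are at most 796 − (days on drug + 30). This bound assumes a first dose on the date of the original protocol; real values are smaller.

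| Days on drug | Counted | Uncounted, full follow-up | Share | Uncounted at 30 Apr 2018, at most | Share |
|---|---|---|---|---|---|
| 182 (6 months) | 212 | 700 of 912 | 76.8% | 584 of 796 | 73.4% |
| 365 (1 year) | 395 | 700 of 1,095 | 63.9% | 401 of 796 | 50.4% |
| 730 (2 years) | 760 | 700 of 1,460 | 47.9% | 36 of 796 | 4.5% |

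For a subject treated to Week 264 in extended access (1,842 days), the full-follow-up share is 700/2,572 = 27.2%. Such a subject would still be on drug at 30 April 2018.

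**3. Collection rules side by side.** Section 6.1.4 closes collection at day 30. Section 5.3.1.1 keeps the adverse event form open at post-treatment follow-up for any change from baseline. The schedules mark the assessment as due at follow-up, yet their footnotes describe those calls as survival contacts. A new skin or lung cancer reported at a month-12 call is recorded under one rule and not under the other.

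**4. What would still show.** SAP 11.3 and protocol 8.1.5.3 summarize deaths more than 30 days after the last dose, and cause of death and later cancer therapies are collected. A fatal or systemically treated second cancer may leave a trace there. A non-fatal one handled by surgery might leave none. No planned output turns these traces into a second-malignancy count.

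**The case against.** **The planned output is correctly labelled.** SAP 11.2 promises the percentage of subjects with a treatment-emergent event, and the protocol and SAP agree on the 30-day cut. A reader might infer that the trial would publish a long-term malignancy rate biased downward. The documents do not support this: no long-term rate is planned or claimed. The objection stands, and the point is an omission from the outputs rather than an error in one of them.

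**The loss at the dated analyses can be small.** This also stands. The table shows that a subject who completes 2 years of treatment loses at most 36 days at the last listed cutoff. Off-drug time is shortened further by death, by withdrawal and by protocol 6.1.1.1, under which clear progression leads to discontinuation from the study. However, SAP 4.5 says remaining data will be collected after that cutoff and sets no different rule for them, so the loss grows as follow-up accrues.

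**The collection rules might be reconciled.** Protocol 5.4.1 continues follow-up of unresolved adverse events, and the post-treatment mark in the schedules could mean only that. This reading explains the mark but not section 5.3.1.1, which covers any change from baseline. The conflict remains, although differing practice between sites is a possibility and not a documented fact.

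**Off-drug cancers are hard to attribute.** Protocol Appendix I lists second cancers among disease-related events in CLL, there is no control arm, and later therapies intervene. That is a reason to show later cases separately. It does not justify leaving them out, given that the SAP chose this event for special attention.

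**Conclusion.** The point holds as a gap in reporting and a conflict in collection. An event of special interest is counted and listed only to day 30 after the last dose, and sites have two rules for what to record afterwards.

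For a subject with complete follow-up, 700 of 730 off-drug days fall outside the count. The effect at any one analysis depends on the cutoff and on when subjects stop: it is largest for early stoppers and close to nil for 2-year completers at 30 April 2018. These figures take each year as 365 days and, for the cutoff column, the earliest conceivable first dose.

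A reader might multiply the planned 250 subjects by nearly two years and an assumed incidence to obtain a number of missed cancers. The documents give neither an incidence nor the follow-up actually achieved, and near-complete off-drug follow-up was impossible for most treatment durations by the last dated cutoff, so no such number is supported. The primary endpoint is unaffected.

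**What to change.** **Protocol.** Give sites one rule. Reconcile section 6.1.4, section 5.4.1 and the follow-up footnotes of Appendices D and E with section 5.3.1.1 and the Post-Treatment columns of those appendices. Whatever is decided for other adverse events, state that second primary malignancies are collected from first dose through the last post-treatment contact.

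**SAP 11.2 and Table 3.** Keep the treatment-emergent count. Beside it add:
- a count and listing of second primary malignancies with onset more than 30 days after the last dose, through last contact or data cutoff;
- follow-up-adjusted (person-time) rates for both periods, because follow-up is very unequal between subjects;
- a split of later cases, and of their person-time, by whether another cancer therapy had started.

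State the cutoff beside each figure. If the question is added after some calls have been made, say from which date it was asked.

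**Cost.** One question on calls already scheduled, one protocol sentence with matching edits to the schedules, and one additional SAP table and listing. Later therapies are already collected, but the split also needs their start dates. The downside is that later cases are harder to attribute to venetoclax; the separate display and the split make that visible but do not resolve it.

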6.1.3 Relationship to Study Drug

The investigator will use the following definitions to assess the relationship of the adverse event to the use of study drug:

Reasonable Possibility	After consideration of factors including timing of the event, biologic plausibility, clinical judgment, and potential alternative causes, there is sufficient evidence (information) to suggest a causal relationship.
No Reasonable Possibility	After consideration of factors including timing of the event, biologic plausibility, clinical judgment, and potential alternative causes, there is insufficient evidence (information) to suggest a causal relationship.

For causality assessments, events assessed as having a reasonable possibility of being related to the study drug will be considered "associated." Events assessed as having no reasonable possibility of being related to study drug will be considered "not associated." In addition, when the investigator has not reported causality or deemed it not assessable, AbbVie will consider the event associated.

If an investigator's opinion of no reasonable possibility of being related to study drug is given, an "Other Cause" of event must be provided by the investigator for the SAE.

[figure not shown]

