8.1.5.1 Adverse Events

Analyses of adverse events will include only "treatment-emergent" events, i.e., those that have an onset on or after the day of the first dose of study drug.

Analyses will not include those that have an onset greater than 30 days after the last dose of study drug.

Treatment-emergent adverse events will be summarized by preferred terms within a System and Organ Class according to the most current MedDRA. In addition, the percentage of subjects experiencing an adverse event at a NCI CTCAE toxicity grade, and relationship to study drug will be provided.

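### SAP 11.2 tabulates events of missing causality as unknown, whereas Protocol 6.1.3 treats them as associated with study drug, so the related-event rate can fall below the protocol's rule

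*SAP*

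**What the plan says.** Protocol 6.1.3 gives the investigator two causality categories. It maps the first to the class the sponsor calls associated: "events assessed as having a reasonable possibility of being related to the study drug will be considered" associated. It then covers the gap: "when the investigator has not reported causality or deemed it not assessable, AbbVie will consider the event associated". An event with no usable assessment thus joins the same class as *Reasonable Possibility*. Protocol 8.1.5.1 makes relationship a planned output ("the percentage of subjects experiencing an adverse event at a NCI CTCAE toxicity grade, and relationship to study drug will be provided") and states no exception to that rule.

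SAP 11.2 sets up the table this way: "Treatment-emergent adverse events will be summarized by relationship of each preferred term to venetoclax, as assessed by the investigator". For an event of "unknown relationship, then the subject will be counted in the relationship category of" *unknown*. It allows one way out: "The only exception is if the subject has another occurrence of the same adverse event with a relationship assessment of" *Reasonable Possibility*. The overview row for related events is defined as "Any treatment-emergent adverse event with reasonable possibility related to venetoclax by the investigator", and the overview lists no unknown line. SAP 13.0 says only that the safety analysis was updated.

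**The concern.** The two documents classify the same event differently. With causality missing, it is associated under the protocol, but in the study tables it sits outside the related column and outside the related overview row. The overview row is the figure most readers will take away on drug-related toxicity. In a single-arm study there is no control group whose rate would shift in parallel, so the related rate stands alone. A rule that can only move that rate down, and that differs from the protocol without saying so, should be reconciled before the tables are read.

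**Working it through.** The plan states no figure on this point, so there is none to reproduce. The check is a comparison of the two rules, followed by the size of the gap per subject.

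**1. The rules side by side.** Take one subject and one preferred term:

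| Subject's occurrences of the term | Protocol 6.1.3 | SAP 11.2 |
|---|---|---|
| At least one *Reasonable Possibility* | associated | *Reasonable Possibility* |
| Causality missing only | associated | *unknown* |
| Missing, plus *No Reasonable Possibility* | associated | *unknown* |
| *No Reasonable Possibility* only | not associated | *No Reasonable Possibility* |

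The rules differ in the second and third rows. In both, the SAP takes the subject out of the related class. No pattern moves a subject the other way.

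**2. Is the protocol rule confined to expedited reporting?** The text does not say so. The rule stands in a paragraph on causality assessment in general and speaks of the event. The sentence after it, on naming another cause, is expressly limited to serious events, so the authors wrote that limit where they wanted it.

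**3. Is this a difference between protocol versions?** The SAP names amendments up to 0.02.01.01 (ROW), and the protocol in hand is one amendment later. That amendment's summary of changes (Protocol 1.1) covers contact details, extended access, signatories and Appendix E, and does not list 6.1.3. The US-only amendments are not in hand.

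**4. Size of the gap.** Let N be the safety population, about 250 (SAP 4.2 for planned enrolment, SAP 5.1.2 for the population). Let r be the subjects with a *Reasonable Possibility* event, and k the subjects with a missing-causality event and no *Reasonable Possibility* event.

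- SAP rate = r/N
- Protocol-rule rate = (r + k)/N
- Gap = k/N, which is never negative

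For one preferred term, k is exactly the count in the *unknown* category, so adding that category back recovers the protocol-rule rate. For the overview row, k counts subjects with a missing-causality event of any term and no *Reasonable Possibility* event of any term. Summing by-term unknowns does not give it, because one subject can appear under several terms and may have a related event under another.

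At N = 250, one subject is 1/250 = 0.4 points:

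| k | 0 | 1 | 5 | 10 | 25 |
|---|---|---|---|---|---|
| Gap (points) | 0 | 0.4 | 2.0 | 4.0 | 10.0 |

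**5. Plausible range, on assumed inputs only.** The documents do not give k.

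- *By term.* Assume 30% incidence, with 1% to 5% of affected subjects in *unknown*: 30% × 1% = 0.3 points, and 30% × 5% = 1.5 points.
- *Overview row.* Assume m independent events per subject, each with causality missing with probability u and, when assessed, rated related with probability p. SAP rate = 1 − [1 − p(1 − u)]^m. Protocol-rule rate = 1 − [1 − p(1 − u) − u]^m. For m = 5, p = 0.2, u = 0.01 these are 66.8% and 68.8%, a gap of 2.0 points.

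| Gap in points | u = 0 | u = 1% | u = 2% | u = 5% |
|---|---|---|---|---|
| m = 5, p = 0.2 | 0 | 2.0 | 4.0 | 9.5 |
| m = 5, p = 0.4 | 0 | 0.6 | 1.3 | 3.1 |
| m = 10, p = 0.4 | 0 | 0.1 | 0.2 | 0.5 |

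The gap shrinks as more subjects already have a related event. The spread shows that no single figure can be defended.

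**The case against.** The best defence is that the passages describe different things. Protocol 6.1.3 says what the sponsor will consider when the investigator is silent, while SAP 11.2 and its overview row are labelled as the investigator's assessment. Showing a missing investigator assessment as unknown is faithful to that label. Missing values should also be uncommon: Protocol 6.1 has the investigator record relationship for each event, and Protocol 10.2 has the eCRFs reviewed for completeness. Most of the other overview rows do not depend on causality, and no efficacy result is touched.

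Much of this stands as a limit on size. It does not remove the conflict. The protocol rule is not restricted to a purpose other than analysis, the SAP presents itself (3.0) as elaborating the protocol's methods, and it does not say it departs from 6.1.3. Nor does the label help with the overview row, where the missing assessments are not shown at all. Within SAP 11.2 itself, an incomplete onset date is resolved conservatively, as treatment-emergent unless evidence confirms otherwise; missing causality is not.

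Two stronger readings might be inferred and are not supported:

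- *That these events are reported as not related.* They go into a separate category that takes precedence over *No Reasonable Possibility* and is visible by term.
- *That rates for events of special interest are biased.* SAP Table 3 defines those by search terms with no causality criterion, and their summaries are not planned by relationship. Such terms are affected only where they also appear in the general relationship table.

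**Conclusion.** The point holds as an undeclared conflict between Protocol 6.1.3 and SAP 11.2 that can act in one direction only. The related rate falls short of the protocol-rule rate by k/N, about 0.4 points per affected subject if N is 250. It falls short only where a subject has an event of missing causality and no related occurrence: of that term in the by-term table, or of any event in the overview row.

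It would be going too far to say that drug-related rates are understated. The documents give no frequency of missing causality, and the gap is zero if there is none. Any shortfall is also measured against the protocol's convention, not against a known true rate. The mismatch and its direction are certain; the size is not known and may be small.

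**What to change.** Replace the unknown-relationship rule in SAP 11.2 with one sentence: an event whose causality is not reported or not assessable is counted as *Reasonable Possibility*, per Protocol 6.1.3, in the relationship tables and in the related-event overview row. Footnote each table with the number of subjects assigned this way, so that the investigator-assessed count can still be read off and the investigator label stays accurate. In the same edit, state the order used when SAP 11.2 selects a subject's most related incident, so that it agrees with the new rule.

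If the sponsor prefers strictly investigator-assessed tables, the minimum is to declare the departure from 6.1.3 and add an overview row that counts unknown as associated.

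The cost is one sentence, a footnote and minor programming, with no new data. Related-event rates become slightly higher wherever causality is missing, and the table label needs the footnote.
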